# 6.8. Management of Elevated Aminotransferase Levels (ALT and/or AST)

If a subject's aminotransferases are elevated, follow the instructions outlined in Table 6.

Table 6: Management of Elevated Aminotransferase Levels (ALT and/or AST)

ALT and/or AST Level(s)	Dose Discontinuation (Yes/No)
> 8× ULN	
> 5× ULN for more than 2 weeks	
> 3× ULN with the appearance of fatigue, nausea, vomiting, right upper quadrant pain or tenderness, fever, rash, and/or eosinophilia (> 5%)	Yes
$> 3 \times \text{ULN } \underline{\text{and}}$ (TBL $> 2 \times \text{ULN } \underline{\text{or}} \text{ INR} > 1.5$ )	
> 3× ULN	No

Abbreviations: ALT=alanine aminotransferase; AST=aspartate aminotransferase; INR=international normalized ratio; TBL=total bilirubin; ULN=upper limit of normal

# 6.9. Management of Study Drug-Related Toxicities

In the case of serious toxicities, the Investigator may choose to interrupt study drug administration. See Section 4.6.2 for details on resuming study drug after interruptions.

## 7. STUDY DRUG

## 7.1. Dose and Treatment Regimens

Study drug is defined as either RTA 901 or placebo. During the Run-in Period, subjects will be administered single-blind placebo once daily in the morning. During the Treatment Period, subjects will be administered double-blind study drug QD in the morning according to their randomized assignment (Table 3).

## 7.2. Identity of Study Drug

RTA 901 drug product information is shown in Table 7. Information about the placebo is shown in Table 8.

**Table 7:** Part 1 RTA 901 Drug Product Information

Description	RTA 901 capsule (10 mg size #4, 40 mg size #0)			
Ingredients	Active Ingredients: RTA 901 Inactive Ingredients: Lactose Monohydrate, Microcrystalline Cellulose, Sodium Starch Glycolate, Magnesium Stearate, Hypromellose Capsule Shell			
Route of Administration	Oral			

**Table 8:** Placebo Information

Description	Placebo for RTA 901 capsule (size #4, size #0)
Ingredients	Active Ingredients: N/A Inactive Ingredients: Lactose Monohydrate, Microcrystalline Cellulose, Magnesium Stearate, Hypromellose Capsule Shell
Route of Administration	Oral

# 7.3. Study Drug Packaging and Labeling

The study drug will be supplied in tamper-evident kits containing high-density polyethylene bottles. Each bottle will utilize foil induction-seal liners and a child-resistant closure. In Part 1, each bottle of study drug will contain 30 capsules of 10 mg or 40 mg strength RTA 901 or the matching placebo capsules. In Part 2, each bottle of study drug will contain 30 capsules of RTA 901 or matching placebo capsules, depending on the doses of RTA 901 recommended by the DSC (see Section 3.6).

In Part 1, the study drug kits will contain a combination of bottles, each containing active or placebo capsules in varying strengths to make up each dosing regimen. Table 9 shows the combination of bottles that will be used to comprise the dose for each treatment arm, while maintaining the study blind in Part 1. Kit configurations for Part 2 will depend on the doses recommended by the DSC. As in Part 1, the kits for each treatment arm will contain the same

number of bottles and the same configuration of capsule sizes necessary to maintain the study blind.

**Table 9:** Study Drug Kit Configurations – Part 1

Treatment Arm	Bottles of 10 mg Size #4 RTA 901	Bottles of Size #4 Placebo	Bottles of 40 mg Size #0 RTA 901	Bottles of Size #0 Placebo
Placebo	0	1	0	2
RTA 901 10 mg	1	0	0	2
RTA 901 80 mg	0	1	2	0

The label on each bottle will contain, at minimum, the following information:

- Medication ID number;
- Protocol 901-C-2102;
- Expiry date;
- Contains 30 capsules;
- Study Drug Caution: New Drug Limited by Federal (or United States) Law to Investigational Use. Keep out of reach of children;
- Control or lot number;
- Store at 15°C to 25°C (59°F to 77°F);
- Reata Pharmaceuticals, Inc., Plano, TX 75024

## 7.4. Study Drug Storage

Clinical study sites must store the study drug in a secure location at 15° to 25°C (59° to 77°F) and maintain a temperature excursion log of the storage conditions. Temperature excursion logs must be available for review at each monitoring visit. If the study drug is stored outside of the designated conditions for 24 hours or more, a temperature excursion notification should be submitted to the Sponsor for review and approval for use of the affected study drug.

# 7.5. Study Drug Administration

Subjects must self-administer 1 capsule orally from each of the bottles included in their study drug kit QD, beginning at Run-in through the end of the Treatment Period, as indicated in Table 4. Each dose of study drug should be administered at approximately the same time each day and will be recorded in the e-diary. All doses should be taken in an early fasted state, defined as having no food within at least 2 hours prior to study drug administration and 1 hour following study drug administration.

A vomited dose must not be replaced. A double dose (eg, missed dose from previous day and dose for current day) must not be taken.

It is the responsibility of the Investigator or designee to provide clear instructions to the subject regarding the number and type of capsules to be ingested at each study drug administration timepoint listed in Table 4. Subjects must be instructed to continue taking study drug once daily through Week 12 unless:

- 1. The subject has been otherwise instructed by the Investigator, or
- 2. The subject has been formally discontinued from study drug.

## 7.6. Treatment Compliance

The Investigator or his/her designated and qualified representatives will only dispense study drug to subjects enrolled in the study in accordance with the protocol. Subjects should administer study drug exactly as instructed by the site. Non-compliance is defined as taking less than 80% or more than 120% of expected study drug during any evaluation period (visit to visit).

Subjects should record in the e-diary all administered and missed doses of study drug. The reason for a missed dose should be recorded in the e-diary. A missed dose includes drug holidays and temporary study drug discontinuations. Subjects will be asked to return all unused study drug (study drug bottles and any unused capsules).

Refer to Section 5.1.7 for compliance related to PRO completion via the e-diary.

## 7.7. Study Drug Accountability

The Investigator, or designee, will maintain a record of all study drug received, dispensed, and returned to the Sponsors' designee. An Investigator or his/her designated representatives will administer the study drug only to subjects enrolled in the study. A current (running) and accurate inventory of study drug will be kept by each Investigator and will include shipping invoices and the date on which study drug is dispensed/administered to the subject. An overall accountability of the study drug will be performed and verified by the study monitor throughout the study and at the closeout visit. Upon completion or termination of the study, all original containers (containing unused study drug) will be returned to the Sponsor or its designee, according to instructions from the Sponsor and according to local regulations. Labels must remain attached to the containers. Local study drug destruction is only allowed with prior Sponsor approval.

## 7.8. Concomitant and Other Treatments

## 7.8.1. Standard of Care Pain Medications

Subjects are required to take only 1 SOC pain medication for neuropathic pain (consistent with regional or local SOC guidelines for DPNP) at a stable dose (defined as < 50% change in total dose) that does not exceed the maximum dose in the prescribing information for approximately 4 weeks prior to Screening. Allowed SOC pain medications include duloxetine, pregabalin, and gabapentin. Attempts should be made to maintain the stable dose of pain therapy. If changes to the dose are necessary, the Investigator should discuss with the Medical Monitor. However, dose

level should not be above the maximum prescribed dose as instructed in the medication's dosage and administration section of the prescribing information.

#### 7.8.2. Allowed Medications

The following medications and therapeutics are allowed during the study:

- Benzodiazepine, zolpidem, diphenhydramine, or related drugs for insomnia if the subject is on a stable dose for 3 months prior to entry and it is not anticipated to change during the study;
- SSRI (selective serotonin reuptake inhibitor) for depression if the subject is on a stable dose for 3 months prior to entry and it is not anticipated to change during the study;
- NSAIDs prescribed for conditions other than DPNP.
- Aspirin ≤325 mg/day for cardiac prophylaxis.
- Rescue medication, see Section 7.8.3.

#### 7.8.3. Rescue Medication

Rescue medication for DPNP is in addition to standard of care medication (gabapentin, pregabalin or duloxetine) for DPNP. Rescue medication is intended to treat temporary elevations in a subject's DPNP and is intended to be used occasionally and not meant to be used for prolonged periods of time.

Subjects who enter screening after implementation of protocol Version 4.0 may only use acetaminophen as a rescue medication for DPNP as needed. If rescue medication is needed for DPNP, subjects will be instructed to take acetaminophen 500 mg every 4 to 6 hours as needed (not to exceed 3000 mg per day).

Subjects currently in the study at the time of implementation of protocol Version 4.0 using ibuprofen as rescue medication for DPNP may switch their rescue medication to acetaminophen (i.e., no longer use ibuprofen as a rescue medication for DPNP) or continue to use as rescue medication for DPNP ibuprofen 200 to 400 mg every 4 to 6 hours as needed (not to exceed 600 mg/day) for up to 3 days in a 7-day period (not calendar week). Subjects unable to comply with these conditions will need to discontinue study treatment and withdraw from the study; some or all of such subjects may be replaced at the discretion of the Sponsor.

The daily maximum dosages stated in this section are inclusive of those used outside of treatment for DPNP. Any questions related to rescue medications should be directed to the Medical Monitor prior to administration when possible.

## 7.8.4. Prohibited Medications

The following medications and therapeutics are prohibited during the study:

 Neuroleptics, monoamine oxidase inhibitors, N-methyl-D-aspartate receptor ligand for pain (ketamine, amantadine, dextromethorphan [except low dose intermittent use for cough], memantine, methadone, dextropropoxyphene, and/or ketobemidone), and/or alpha-lipoic acid;

- Tricyclic antidepressants and other tricyclic drugs including cyclobenzaprine and promethazine; triptans (prescribed usage outside of DPNP allowed); and/or 5-HT3 receptor antagonists;
- Drugs or chemicals that may cause neuropathy and interfere with clinical evaluation.
   Agents include but are not limited to pyridoxine, hydralazine, metronidazole,
   phenytoin, dapsone, amiodarone, nitrofurantoin, paclitaxel, vinblastine, vincristine,
   cisplatin, etoposide, didanosine, disulfiram, suramin, zalcitabine, anti-tuberculosis
   medications (eg, isoniazid, rifampin, ethambutol, ethionamide), heavy metals, and
   industrial solvents;
- Strong or moderate CYP3A4 inhibitors or inducers and P-gp inhibitors;
- Topical pain medications intended to treat pain associated with DPNP (including but not limited to lidocaine 5% patch, over-the-counter capsaicin, amitriptyline, and/or isosorbide dinitrate spray);
- Prescription patch containing 8% capsaicin;
- Opioid or opioid based drugs;
- Central nervous system active drugs such as cocaine, amphetamines, and cannabinoids (marijuana);
- Oral prednisolone or equivalent are excluded during the Screening and Run-in Periods;
- NSAIDs for DPNP (applies only to subjects who enter the study following implementation of protocol Version 4.0) (see Section 7.8.2 for NSAIDs prescribed for conditions other than DPNP):
- Muscle relaxers.

### 7.8.5. Prohibited Devices/Procedures

- TENS unit for the treatment of DPNP;
- Implantation of neurostimulators;
- Nerve decompression surgery for treatment of DPNP;
- Steroid or local anesthetic nerve blocks;
- Cryotherapy, intrathecal/epidural opioids, or botulinum toxin;
- Alternative medicine products or treatments (eg, acupuncture, naturopathy, homeopathy, etc.).

## 7.8.6. Recording of Concomitant Treatment

Concomitant medications include those being taken at Screening or at any point throughout the study, up to and including the Week 16/EOS visit. Instructions to discontinue any medication to comply with the study protocol should take place only after the subject has signed the ICF. Concomitant medication will be recorded on eCRFs by their trade and/or generic name and will include dose and duration of treatment. Subjects requiring excluded medications will not be

eligible for the study. Planned deviations from the eligibility criteria, with regard to excluded medications, will not be approved. Subjects will be instructed to consult with the Investigator or other site personnel before taking any newly prescribed medications, over-the-counter medications, or supplements/herbal preparations. If a subject requires use of a prohibited medication during the study, the Medical Monitor should be contacted to determine whether an alternative drug is feasible and if not, how to handle dosing with study drug while the prohibited medication is being used. Documentation of these discussions must be maintained in the subject's source records.

### 8. STATISTICS

### 8.1. Sample Size Estimate

This study will be conducted in 2 parts. A total of approximately 192 subjects (64 subjects per treatment arm) are planned for randomization in Part 1 and approximately 192 subjects (64 subjects per treatment arm) are planned for randomization in Part 2, for a total of 384 subjects to be randomized. This sample size is based on a dose-ranging scheme to evaluate initial safety, efficacy, of RTA 901 in this population. The primary comparisons for efficacy are between each of the 2 RTA 901 treatment groups and the placebo treatment group. The overall Type I error rate will be controlled at the 0.05 significance level. A hierarchical testing strategy to control the overall Type I error will be defined in the SAP. Power calculations are based on a 2-sample t-test with no adjustments for multiple comparisons. The study assumes a difference in NPRS pain intensity means of 1.2 between each RTA 901 treatment group and the placebo treatment group and a standard deviation of 2.4.

If doses selected for Part 2 do not include doses studied in Part 1, then an analysis by dose group for Part 1 or Part 2 doses will be performed following completion of each study part. Within each Part, with 64 subjects per treatment group, each study part has 80% power to compare treatment groups to placebo.

If doses selected for Part 2 include any doses studied in Part 1 (ie, 10 or 80 mg), then an analysis by dose group will be performed using Part 1 and Part 2 combined, following completion of the study. The dose group that is enrolled in both parts will have 128 subjects. With 128 placebo subjects compared to 128 subjects in the RTA 901 dose group, there is 98% power to detect the same difference (1.2 NPRS points) assuming the same standard deviation (2.4). RTA 901 dose groups that are enrolled in only 1 part will have 64 subjects. With 128 placebo subjects compared to 64 subjects in each RTA 901 dose group, there is 90% power to detect the same difference (1.2 NPRS points) assuming the same standard deviation (2.4).

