## 3.6. Part 2 Dose Selection Process

A Dose Selection Committee (DSC) comprised of Sponsor personnel and an external pharmacometrics consultant will select the 2 doses of RTA 901 for Part 2 using data from Part 1. An E-R analysis for efficacy will be conducted with efficacy data from all subjects up to Week 12 of treatment in Part 1 and provide a dosing recommendation for Part 2 to the DSC. The selected doses will be documented in a Note-to-File to the Investigators and IRBs (as appropriate) and will not require a protocol amendment.

It is possible that enrollment in Part 2 of the study may begin while some Part 1 subjects are completing their remaining study visits. Subjects enrolled in Part 1 will not be eligible for enrollment in Part 2.

Details of the membership, objectives, and process to be followed by the DSC will be described in a separate charter. Additionally, a separate data management and analysis plan supporting this activity will be created. Results will be reported in a separate standalone report, outside the clinical study report (CSR).

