### 4.5.2.3. Dose Selection Committee

The DSC will be comprised of Sponsor personnel and an external pharmacometrics consultant. The E-R analysis will be conducted for efficacy using unblinded data from all subjects in Part 1, which is the basis for dosing recommendation of Part 2 to DSC. Eligible doses for selection in Part 2 will be limited to a dose range of 1 to 80 mg of RTA 901. The selected doses will be documented in a Note-to-File to the Investigators and IRBs (as appropriate) and will not require a protocol amendment.

Details of the membership, objectives, and process to be followed by the DSC will be described in a separate charter. Additionally, a separate data management and analysis plan supporting this activity will be created. Results will be reported in a separate standalone report, outside the CSR.

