### 8.4.6. Interim Analysis

No interim analysis for efficacy or safety is planned.

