TEAE	treatment-emergent adverse event
TENS	transcutaneous electrical nerve stimulation

Product: RTA 901 (BIIB143)Statistical Analysis PlanStudy: 901-C-2102Version: 1.0

1. Introduction

Study 901-C-2102 is a 2-part, randomized, placebo-controlled, double-blind, Phase 2 study to evaluate the safety, tolerability, efficacy, of RTA 901 in qualified subjects with diabetic peripheral neuropathic pain (DPNP). Approximately 192 eligible subjects (64 subjects per treatment arm) will be enrolled in Part 1. Randomization within each part will be stratified by SOC pain medication using randomization and trial supply management (RTSM). The doses for Part 2 will be selected based on Part 1 data. Potential changes with study design for Part 2 may also apply pending the Part 1 results.

The purpose of this Statistical Analysis Plan (SAP) is to describe the planned analyses for Part 1 safety, tolerability, efficacy, of RTA 901 up to the Part 1 end of study visit (Week 16). A separate statistical analysis plan will be prepared for Part 2.

This SAP is based on Version 4 of the protocol, dated 9 MAY 2024. All references to the protocol refer to Version 4. This SAP will cover the planned analysis only for Part 1.

2. Study Overview

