2.4. Sample Size Considerations

This sample size for Part 1 is based on a dose-ranging scheme to evaluate initial safety, efficacy, of RTA 901 in patients with DPNP. The primary comparisons for efficacy are between each of the 2 RTA 901 treatment groups and the placebo treatment group. With assumed treatment difference of 1.2 and standard deviation of 2.4 in NPRS pain intensity, 64 subjects per arm approximately provides 80% power with two-sided alpha of 0.05. The purpose of Part 1 is to provide dose selection information for Part 2.

3. Definitions

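### A Part 1 dose reused in Part 2 is analysed on pooled data that include the unblinded Part 1 results used to choose it, and no adjustment for that selection is specified

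*Protocol*

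**What the plan says.** **Choice of dose.** Under Protocol 3.6 a Dose Selection Committee "will select the 2 doses of RTA 901 for Part 2 using data from Part 1". Protocol 4.5.2.3 adds: "The E-R analysis will be conducted for efficacy using unblinded data from all subjects in Part 1". Protocol 4.5.1 confirms that its members are unblinded. No numerical selection rule appears; the process is left to a separate charter and analysis plan.

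**Analysis of a reused dose.** If Part 2 includes 10 or 80 mg, Protocol 8.1 provides that "an analysis by dose group will be performed using Part 1 and Part 2 combined, following completion of the study", and Protocol 8.3 places that analysis after the final database lock. The power quoted for such a dose is 98%, from 128 against 128 subjects. Protocol 8.1 states: "Power calculations are based on a 2-sample t-test with no adjustments for multiple comparisons".

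**Error control.** Protocol 8.1 promises: "The overall Type I error rate will be controlled at the 0.05 significance level". The only means named, there and in 8.4.2, is a hierarchical strategy to be set out in the SAP. The SAP supplied covers Part 1 alone; its Introduction says: "A separate statistical analysis plan will be prepared for Part 2". Protocol 8.4.6 states: "No interim analysis for efficacy or safety is planned".

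**The concern.** This branch of the design selects a dose on its observed outcome and then returns the same outcome data to the confirmatory comparison. A dose carried forward partly because of a lucky Part 1 keeps that luck in half of its final sample. A fixed order of hypotheses controls which tests may be made. It does not change the distribution of a pooled difference whose first half was selected.

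The study is meant to identify the dose or doses for further development (Protocol 1.2), so the pooled estimate for a reused dose is the figure a reader would rely on most. The stated 98% power is that of a fixed 128 versus 128 comparison and makes no allowance for selection.

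**Working it through.** **Inputs.** Difference 1.2, SD 2.4 and 64 per arm per part (Protocol 8.1); 1:1:1 randomisation with one placebo arm in each part (Protocol 4.5). Two-sided 0.05, hence 2.5% on the benefit side, is stated for Part 1 in SAP 2.4 ("64 subjects per arm approximately provides 80% power with two-sided alpha of 0.05") and is assumed here for the pooled test. The selection rules below are assumptions. No dropout is applied, because Protocol 8.1 gives no rate.

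**1. The plan's own power figures.** SE = 2.4 × √(1/n₁ + 1/n₂); approximate power = Φ(1.2/SE − 1.96).

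| Comparison | SE | 1.2/SE | Power, normal | Power, t-test | Stated |
|---|---|---|---|---|---|
| 64 v 64 | 0.424 | 2.83 | 80.7% | 80.2% | 80% |
| 128 v 128 | 0.300 | 4.00 | 97.9% | 97.9% | 98% |
| 64 v 128 | 0.367 | 3.27 | 90.4% | 90.1% | 90% |

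All three reproduce, so they are the powers of plain pooling with no selection.

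**2. Bias when the better Part 1 dose is always reused, no true effect.** The two Part 1 differences share a placebo arm, so their correlation is 0.5. The expected maximum of two such standard normal variables is √((1 − 0.5)/π) = 0.399. The Part 1 bias is 0.399 × 0.424 = 0.169. Part 2 is unbiased and has equal weight, so the pooled bias is 0.169/2 = 0.085 points, or 0.085/1.2 = 7% of the assumed effect.

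**3. Error rates by selection rule, no true effect.** Simulation with normal arm means (4 million or more trials), testing the reused dose with z = pooled difference/0.300 against 1.96. Overall error = P(reuse) × error given reuse.

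| Rule | P(reuse) | Benefit-side error given reuse | Overall benefit-side error | Bias given reuse |
|---|---|---|---|---|
| Better dose, always | 1.00 | 4.0% | 4.0% | +0.085 |
| Better dose, if Part 1 difference > 0 | 0.67 | 6.0% | 4.0% | +0.19 |
| Better dose, if > 0.3 | 0.37 | 10.2% | 3.7% | +0.28 |
| Better dose, if > 0.6 | 0.13 | 20.4% | 2.7% | +0.40 |
| One fixed dose, if > 0 | 0.50 | 4.9% | 2.5% | +0.17 |
| One fixed dose, whatever its result | 1.00 | 2.5% | 2.5% | 0 |
| Both doses, 80 then 10 mg | 1.00 | 2.5% | 2.5% | 0 |
| Worse dose, always | 1.00 | 0.9% | 0.9% | −0.085 |

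In the first row the opposite tail falls to 0.9%, so the two-sided total stays at about 5.0%.

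**4. With true effects, better dose always reused.** If both doses have an effect of 1.2, the bias is again +0.085. If only 80 mg works, it is almost always selected and the bias is about 0.

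**5. Adjusted methods, same rule.** The example tested is an equal-weight inverse-normal combination, z = (z₁ + z₂)/√2, in a closed test with a Dunnett-adjusted Part 1 intersection. Its benefit-side error is 2.5%. Power is 96.5% if one dose works (97.8% with plain pooling) and 98.7% if both do (99.2%). Part 2 data alone also gives 2.5%, with no bias and power of about 80%.

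**The case against.** The strongest reply is that the method is unspecified, not wrong. Protocol 8.1 uses a t-test only for power; the primary analysis is an MMRM (8.4.3). Overall type I error control is promised, the SAP is the final arbiter (8.3), and the Part 2 SAP could supply an adjustment. Protocol 1.4 also suggests that Part 2 may look below 10 mg, so a strong 10 mg result might not lead to reuse at all. All of this is fair. It means the error rate cannot be called inflated as a matter of fact. It does not remove the point: the pooling rule is already in the protocol, and following it after outcome-based selection can bias the estimate whatever test order is later chosen.

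A reader might draw three stronger conclusions that the documents do not support:

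- **That upward bias and excess false claims are certain.** Both depend on a rule held in a charter that is not supplied. Several plausible rules give no inflation, and one gives a downward bias.
- **That the type I error reaches 6%, 10% or 20%.** Those rates are conditional on reuse. The matching overall rates are 4.0%, 3.7% and 2.7%. Only the overall rate is what the protocol undertakes to control.
- **That the Part 2 SAP will be written after Part 1 is unblinded.** The SAP gives no date for it.

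The 4.0% figure also reads the test on its benefit side. The directional hypothesis in Protocol 8.4.1 makes that reasonable, but the only level the SAP states is two-sided, and on that basis the total is still about 5% under the always-better rule.

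**Conclusion.** The point stands as a conditional gap that is cheap to close. It applies only if 10 or 80 mg is reused, and its size depends on how the dose is picked. Among the rules examined, the overall benefit-side error with no true effect runs from 0.9% (worse dose reused) to 4.0% (better dose reused), against 2.5%. Bias given reuse runs from −0.085 to +0.40 points. The +0.40 case is one third of the assumed effect of 1.2, but under that rule reuse happens in only about 13% of null trials.

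The estimate is the more persistent problem. Reusing a fixed dose only when it looks promising leaves the overall error at or below 2.5% yet still biases the estimate upward. These figures rest on normal means, 64 per arm with complete data, and a two-sided 0.05 pooled test.

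**What to change.** Before Part 1 results are unblinded to the committee, state in Protocol 8.1 and 8.3, or in the Part 2 SAP, that a reused dose will be tested by a prespecified selection-adjusted method. Two options are:

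- a closed inverse-normal combination of the two parts with equal weights √(1/2), using intersection tests in each part that cover every dose tested there. This must extend to two reused doses, new Part 2 doses, and a dose studied in one part but compared with 128 pooled placebo subjects; or
- Part 2 data alone for the reused dose.

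Whichever is chosen:

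- report the Part 2-only estimate beside the pooled one;
- say in Protocol 8.4.6 that the Part 1 exposure-response analysis is an unblinded efficacy look in this branch;
- restate the 98% power for the chosen method. Under the better-of-two rule that is about 96.5% (one dose works) or 98.7% (both work) with the combination test, and about 80% with Part 2 alone.

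The cost is wording and slightly more analysis work. Power falls by about 1 point with the combination test (97.8 − 96.5 = 1.3; 99.2 − 98.7 = 0.5), and by far more if only Part 2 is used. No extra subjects or visits are needed.
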